7.2.9 Monitoring of Other Participating Institutions

Monitoring visits are done remotely unless otherwise specified, via remote EMR access. If not possible, secure email exchange will be utilized. The quality assurance specialist will confirm an upcoming monitoring visit with a Site Investigator and staff. If remote EMR access is not available, then the Site Coordinator will ensure that all source documents for subjects are de-identified and labeled only with the subject ID number(s), and emails all requested documents to the quality assurance specialist by the specified visit date. All documents are reviewed and a monitoring report is submitted within 5 business days from the date of the visit. Any outstanding documents will be listed in the report as a high- priority request for the next monitoring visit. It is expected that response to data clarification requests and other trial-related inquiries will occur throughout the course of the study through regular

communication with the site monitor, the Sponsor or representatives, and review/entry of data into the electronic study database. Continued non-compliance and failure to submit documentation will result in the suspension of subject enrollment at the site, until the documents have been received.

8.0 STATISTICAL ANALYSIS PLAN

8.1 Statistical Analysis Plan

The Simon optimal two-stage design to test the null hypothesis of <10% RR (CR+PR) versus the alternative hypothesis of >30% overall response rate requires an overall sample size of 29 subjects in order to achieve 80% power with a significance level of 5%. After testing the combination therapy on 10 response evaluable subjects in the first stage, the trial will be terminated if there are 1 or fewer responses. If there are 2 or more responses (including non-confirmed responses) the trial will continue on to second stage. A response evaluable subject is defined as having received both investigational agents for at least 2 cycles and had one CT scan for disease evaluation on therapy, or evidence of early (prior to 2 cycles) clear progression on physical examination, or death prior to 2 cycles. Best overall response for the interim analysis will be assessed up to 6 months on treatment. If the trial goes on to the second stage, then if there are 5 or fewer responses out of 29 response evaluable subjects, the combination therapy will be rejected. If there are 6 or more responses (including non-confirmed responses) over the entire treatment duration - the combination will be studied further.

At the end of the study, toxicities, as measured by the NCI CTCAE Version 4.03, will be described by frequency and grade, by cycle and over all cycles, with the maximum grade over all cycles used as the summary measure per patient. Overall response rates (defined as PR plus CR) will be estimated with exact 95% confidence intervals. PFS and OS will be described using Kaplan-Meier curves.

All subjects who receive at least one dose of the lenvatinib and/or pembrolizumab combination will be evaluable for toxicity.

Efficacy Measures

Response rate (RR): Best overall response will be calculated as the best response (CR or PR) recorded from the start of treatment for each subject, and will be used for the summaries of objective response. Best overall response will be determined programmatically based on the RECIST 1.1 criteria. For this study confirmation of response within 4 weeks will not be required.

Progression Free Survival (PFS): is defined as the interval between the date of start of treatment and the earlier date of objective disease progression per RECIST 1.1 criteria or death due to any cause in the absence of progression.

Product: Pembrolizumab/MK-3475

Protocol/Amendment No.: May 18, 2020v2.0

Overall Survival (OS): is calculated as the interval from the start of treatment to the date of subject death (any cause).

RECIST 1.1 assessments (including Target Lesion measurements) will be used to determine ORR and PFS. Imaging assessments will be made every 6-9 weeks.

Safety Measures

AEs and SAEs will be collected throughout the study from informed consent until 30 days after study treatment is discontinued. Investigators must continue to report all SAEs to the NYU CTO until 30 days after study treatment is discontinued.

If a subject discontinues study treatment for reasons other than disease progression, and therefore continues to have tumor assessments using RECIST following the 30 days after the last dose of the last study treatment, only study drug-, or study procedure-related SAEs will be captured until the subject is considered to have progressive disease.

AEs will be graded according to the National Cancer Institute Common Terminology Criteria for AEs.

AEs will be coded using MedDRA (Medical Dictionary for Regulatory Activities).

Biomarker/Exploratory Objectives

All biomarker analyses will consist of descriptive statistical summaries at baseline (means, medians, standard deviations, quantiles, ranges, etc.) and graphical displays (e.g. boxplots). Similar summaries will be provided by changes from baseline and response status for each of the biomarkers under study. We will use non-parametric tests to assess the relationships between PDL1 status, gene expression profiles of interest, and response to combination treatment of pembrolizumab and lenvatinib. Outcome relationships will be largely explorative and descriptive.

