5.8 Subject Replacement Strategy

There are no replacement subjects allowed.

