and will be performed approximately every 6-9 weeks. Timing of imaging will be based on the start of pembrolizumab on cycle 1, day 1. First imaging assessment will be done at 6 weeks, prior to cycle 3, day1. Next assessment will be done six weeks thereafter, prior to cycle 5, day1. Subsequent imaging will be done every 3 cycles (9 weeks) thereafter, ie prior to cycle 8, 11, 14 etc.

^kArchived tumor specimens will be collected at study enrollment. Receipt of specimens is not required prior to initiating study treatment.

^lBlood for correlative studies will be collected on Day 1 of lead in of lenvatinib and day 1 of Cycle 1 and on Day 1 of Cycle 2. Blood will be collected before administration of study treatment.

^mSubjects who attain a CR or complete 24 months of treatment with pembrolizumab may discontinue treatment with the option of restarting treatment. Subjects who stop pembrolizumab with stable disease may continue treatment for up to 1 year if progression occurs after stopping study treatment, if the study remains open and the conditions in section 7.1.5.3.5 are met.

ⁿFollow-Up: Subjects who discontinue study therapy for a reason other than disease progression will undergo radiologic assessment every 9 weeks (63 ± 7 Days) to monitor disease status. Throughout the Follow-Up period, information regarding disease status, subsequent antineoplastic therapy, and survival status will be collected.

^oSurvival Follow-Up will occur via telephone call every 12 weeks until death, withdrawal of consent, or end-of-study, whichever occurs first.

^pAt Screening only, unless as clinically indicated

^qWithin 72 hours prior to C1D1

Product: Pembrolizumab

Protocol/Amendment No.: May 18, 2020v2.0

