7.1.5.3.3 Follow-up Visits

Study subjects will receive up to 24 months of Pembrolizumab, and then will continue on Lenvatinib only. Subjects will then be followed every 9 weeks (\pm 7 days) with radiologic imaging (CT scan or MRI). If a subject experiences disease progression on single agent lenvatinib, then that subject will have the option to restart Pembrolizumab if all the other criteria are met (please see section 7.1.5.3.5 below entitled “Second Course Phase (Retreatment Period)” for more information).

Every effort should be made to collect information regarding disease status until the start of new anti-neoplastic therapy, disease progression, death, end of the study or if the subject begins retreatment with pembrolizumab as detailed in Section 7.1.5.3.5. Information regarding post-study anti-neoplastic treatment will be collected if new treatment is initiated.

Subjects who are eligible to receive retreatment with pembrolizumab according to the criteria in Section 7.1.5.3.5 will move from the follow-up phase to the Second Course Phase when they experience disease progression. Details are provided in Section 6.0 – Trial Flow Chart for Retreatment.

The following will be performed at **Follow-Up Visits** (every 6-8 weeks after study treatment discontinuation):

Product: Pembrolizumab

Protocol/Amendment No.: May 18, 2020v2.0

- Collection of Demographic Information and Medical History
- Collection of Prior and Concomitant Medication Information
- Collection of Adverse Event Information
- Physical Examination
- Vital Signs
- ECOG Performance Status
- CBC with Differential
- Comprehensive Serum Chemistry Panel
- Thyroid Function Tests (T3, FT4, and TSH)
- Tumor Imaging and Disease Assessment
- Collection of Post-Study Antineoplastic Therapy Information
- Collection of Survival Status Information

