13.2 Common Terminology Criteria for Adverse Events V4.03 (CTCAE)

The descriptions and grading scales found in the revised NCI Common Terminology Criteria for Adverse Events (CTCAE) version 4.03 will be utilized for adverse event reporting. (<http://ctep.cancer.gov/reporting/ctc.html>)

13.3 Response Evaluation Criteria in Solid Tumors (RECIST) 1.1 Criteria for Evaluating Response in Solid Tumors

RECIST version 1.1* will be used in this study for assessment of tumor response. While either CT or MRI may be utilized, as per RECIST 1.1, CT is the preferred imaging technique in this study.

* As published in the European Journal of Cancer:

E.A. Eisenhauer, P. Therasse, J. Bogaerts, L.H. Schwartz, D. Sargent, R. Ford, J. Dancey, S. Arbuck, S. Gwyther, M. Mooney, L. Rubinstein, L. Shankar, L. Dodd, R. Kaplan,

D. Lacombe, J. Verweij. New response evaluation criteria in solid tumors: Revised RECIST guideline (version 1.1). Eur J Cancer. 2009 Jan;45(2):228-47.

In addition, volumetric analysis will be explored by central review for response assessment.

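### After 2 cycles a subject counts as response-evaluable only with an on-therapy CT scan, so a later death before the scan or a valid MRI assessment drops out of the response denominator (minor)

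*Combined protocol and SAP*

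**What the plan says.** Section 8.1 sets a Simon optimal two-stage design on response-evaluable subjects. It stops with 1 or fewer responses among the first 10 and rejects the combination with 5 or fewer among 29. The same term defines both denominators. There are three routes to being evaluable:

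- the subject "received both investigational agents for at least 2 cycles and had one CT scan for disease evaluation on therapy";
- before 2 cycles, clear progression on physical examination;
- death before 2 cycles.

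The last two are given together as early "clear progression on physical examination, or death prior to 2 cycles".

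Other sections bear on this:

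- Section 6.0, imaging footnote: "First imaging assessment will be done at 6 weeks, prior to cycle 3, day1". The timing runs from the first pembrolizumab dose.
- Section 13.3: "While either CT or MRI may be utilized, as per RECIST 1.1, CT is the preferred imaging technique in this study". Section 7.1.2.5 also admits MRI, as the least preferred option.
- Section 5.7: subjects who stop treatment without progression continue to be followed for disease status.
- Section 5.8: "There are no replacement subjects allowed". The Trial Summary plans 29 subjects.

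**The concern.** Once a subject has passed 2 cycles, the on-therapy CT is the only way into the denominator. Three kinds of subject can fall out:

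1. One who dies or clearly progresses on examination after 2 cycles but before the first scan. Two nearly identical deaths on either side of the 2-cycle mark are then treated in opposite ways: the earlier is a non-response, the later disappears.
2. One whose first scan falls after the last dose, so that it is arguably not on therapy. The plan collects that scan but does not let it confer evaluability.
3. One assessed only by MRI. The protocol accepts this as a RECIST 1.1 assessment, but the definition does not.

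The first group are non-responders, and the second probably mostly so. Removing them can only raise the observed response rate. The third group may include responders, so valid data are lost. Since 29 are planned and 29 evaluable are needed, there is no spare subject.

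**Working it through.** **Inputs.** From section 8.1: null rate 10%, alternative 30%, 10 subjects in stage 1 (continue with 2 or more responses), 29 in total (go with 6 or more). From section 2.2: a cycle is 21 days. The fraction q of subjects dropped is not in the documents. I assume 3%, 5% and 10%, or roughly 1 to 3 of 29.

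**Step 1: reproduce the design.**
P(go | p) = sum over x = 2 to 10 of b(x; 10, p) × P[Bin(19, p) ≥ 6 − x].

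- At p = 0.10, the terms for x = 2 to 6 are 0.0223 + 0.0169 + 0.0065 + 0.0013 + 0.0001 = 0.0471; terms for larger x are negligible.
- At p = 0.30, the sum is 0.8051.

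A search for the smallest expected sample size under the null, with type I error at most 5% and power at least 80%, returns the same bounds. The design figures are correct. The issue is who is counted.

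**Step 2: the reported response rate.** Suppose 6 responses among 29 and two non-responders removed. The rate moves from 6/29 = 20.7% (exact 95% CI 8.0-39.7) to 6/27 = 22.2% (8.6-42.3). This takes the reported rate to be computed on the response-evaluable set; section 8.1 names no other efficacy denominator.

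**Step 3: non-responders dropped, 29 enrolled, nobody replaced.** Let p be the rate among all treated. The rate among evaluable subjects is p_e = p/(1 − q), and the number evaluable is m ~ Bin(29, 1 − q). Stage 1 is the first 10 evaluable. Then
P(go) = sum over m ≥ 10 of P(m) × sum over x ≥ 2 of b(x; 10, p_e) × P[Bin(m − 10, p_e) ≥ 6 − x].

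| q | P(go) at p = 0.10 | P(go) at p = 0.30 |
|---|---|---|
| 0 | 4.7% | 80.5% |
| 3% | 4.8% | 81.7% |
| 5% | 4.9% | 82.4% |
| 10% | 5.1% | 84.2% |

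The change is small because the final rule is a count of responses, and removing non-responders does not change that count. Only the make-up of the first 10 shifts.

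**Step 4: non-responders dropped, enrolment continued to 29 evaluable.** Put p_e into the step 1 formula. For q = 3%, 5% and 10%, p_e = 0.1031, 0.1053 and 0.1111, and type I error is 5.3%, 5.8% and 7.1%.

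**Step 5: loss unrelated to response, not made up.** This is the MRI-only case. With 10 in stage 1, unchanged cut-offs and 28, 27 or 26 evaluable in total, power is 79.3%, 77.9% or 76.1%, and type I error is 4.2%, 3.7% or 3.2%.

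**Step 6: how wide the death window is.** Two cycles are 2 × 21 = 42 days, or 6 weeks, and the first scan is due at 6 weeks. If 2 cycles means two completed cycles, the window opens only when the scan is late or missed. If it is met once the cycle 2 doses have been given, the window is up to about 3 weeks. Section 8.1 does not say which.

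**The case against.** The strongest reply is that the gap is narrow and nearly harmless, and much of that stands.

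- On the completed-cycles reading, a subject must have a late or missed scan and also die or progress in that interval.
- MRI-only subjects should be rare. Sections 6.0 and 7.1.2.5 call for CT of chest, abdomen and pelvis and prefer non-contrast CT to MRI. A chest CT beside an abdominal MRI might also satisfy the definition. The mention of CT or MRI in section 7.1.5.3.3 concerns later follow-up imaging and adds little.
- On therapy is undefined. Lenvatinib is daily, and section 5.3.1.2 keeps a subject on study on the remaining agent when the other is stopped for toxicity, so few first scans need fall outside it.
- The definition also omits subjects who stop before 2 cycles for toxicity, withdrawal or progression seen only on imaging. They may be more numerous, and this fix does not reach them.

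A reader might infer that false-positive risk rises to about 7% while power also falls below 80%. The documents do not support that. The 7.1% needs enrolment refilled to 29 evaluable, which the Trial Summary and section 5.8 do not provide for. The power loss needs the opposite, no refilling, and loss unrelated to response. When the subjects lost are non-responders and nobody is replaced, the chance of a go at a 30% rate rises slightly.

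What remains is the wording: nothing elsewhere counts a late death without a scan as a non-response or accepts MRI for evaluability.

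**Conclusion.** The point holds as a minor defect of definition. Section 8.1 sets an arbitrary cut at 2 cycles for counting deaths and clinical progressions, and names one imaging method where the protocol allows two. The direct consequence is an upward bias in the response rate, about 1.5 percentage points (22.2% − 20.7%) in the example of two non-responders removed.

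The effect on the decision rule depends on accrual. With 29 enrolled and none replaced, which is how the documents read, type I error goes from 4.7% to 4.8-5.1%. If enrolment were extended to 29 evaluable, it would be 5.3-7.1%. If one subject is lost for reasons unrelated to response, leaving 28 evaluable with the first stage still at 10, power goes from 80.5% to 79.3%. These are separate scenarios. The error-rate ranges rest on the assumed 3-10% loss, for which the documents give no figure.

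**What to change.** In section 8.1:

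- Replace the requirement for one on-therapy CT scan with: *had at least one post-baseline RECIST 1.1 tumour assessment (CT or MRI) before any new anti-cancer therapy*.
- Replace the two routes limited to the period before 2 cycles with: *death or clear clinical progression before the first post-baseline tumour assessment, at any time*, counted as non-response.

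This is a wording change only, with no new data collection and no change to the design bounds. The cost is a slightly lower reported response rate, because a few more non-responders stay in the denominator.

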7.0 TRIAL PROCEDURES

7.1 Trial Procedures

The Study Flow Chart - Section 6.0 summarizes the trial procedures to be performed at each visit. Individual trial procedures are described in detail below. It may be necessary to perform these procedures at unscheduled time points if deemed clinically necessary by the investigator.

Furthermore, additional evaluations/testing may be deemed necessary by the Sponsor and/or Merck and/or Eisai for reasons related to subject safety. In some cases, such evaluation/testing may be potentially sensitive in nature (e.g., HIV, Hepatitis C, etc.), and thus local regulations may require that additional informed consent be obtained from the subject. In these cases, such evaluations/testing will be performed in accordance with those regulations.

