- **Complete Response** - Disappearance of all target lesions. Any pathological lymph nodes (whether target or non-target) must have reduction in short axis to < 10 mm (the sum may not be “0” if there are target nodes).
- **Partial Response** - At least a 30% decrease in the sum of the diameters of target lesions, taking as reference the baseline sum diameters.
- **Progressive Disease** - At least a 20% increase in the sum of diameters of target lesions, taking as reference the smallest sum on study (this includes the baseline sum if that is the smallest on study). In addition to the relative increase of 20%, the sum must also demonstrate an absolute increase of at least 5 mm. (Note: The appearance of one or more new lesions may be considered progression.)
- **Stable Disease** - Neither sufficient shrinkage to qualify for PR nor sufficient increase to qualify for PD, taking as reference the smallest sum of diameters while on study.

Evaluation of Non-target Lesions

Product: Pembrolizumab

Protocol/Amendment No.: May 18, 2020v2.0

- **Complete Response** - Disappearance of all non-target lesions and normalization of tumor marker level. All lymph nodes must be non-pathological in size (< 10 mm in short axis).
- **Non-complete Response/Non-progressive Disease** - Persistence of 1 or more non-target lesion(s) and/or maintenance of tumor marker level above the normal limits.
- **Progressive Disease** - Unequivocal progression of existing non-target lesions will be defined as the overall level of substantial worsening in non-target disease such that, even in presence of SD or PR in target disease, the overall tumor burden has increased sufficiently to merit discontinuation of therapy. In the absence of measurable disease, change in nonmeasurable disease comparable in magnitude to the increase that would be required to declare PD for measurable disease. Examples include an increase in a pleural effusion from “trace” to “large,” an increase in lymphangitic disease from localized to widespread.

Appearance of New Lesions

The appearance of new lesions is considered PD according to RECIST v1.1. Considering the unique response kinetics that have been observed with immunotherapy, new lesions may not represent true disease progression. In the absence of rapid clinical deterioration, subjects may continue to receive study treatment until confirmed PD.

Evaluation of Overall Response

Treatment of subjects may continue

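### The response-evaluable definition in section 8.1 has no route for early progression shown on CT, so a known non-responder can drop out of both decision sets

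*Combined protocol and SAP*

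**What the plan says.** Section 8.1 sets up a Simon optimal two-stage design to "test the null hypothesis of <10% RR (CR+PR) versus the alternative hypothesis of >30% overall response rate", and "requires an overall sample size of 29 subjects". Both decision bounds are counted in response-evaluable subjects: stop at 1 or fewer responses among the first 10, and reject at 5 or fewer among 29.

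The same section gives three routes to being response evaluable:

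1. "having received both investigational agents for at least 2 cycles and had one CT scan for disease evaluation on therapy";
2. before 2 cycles, clear progression found on physical examination;
3. before 2 cycles, death.

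The second and third routes read in full: "evidence of early (prior to 2 cycles) clear progression on physical examination, or death prior to 2 cycles". CT is named only in the first.

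Other relevant text:

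- **Timing of CT.** The imaging footnote to the Study Flow Chart (section 6.0) puts the first scan at 6 weeks from Cycle 1 Day 1, before Cycle 3 Day 1. Section 7.1 allows earlier scans: "It may be necessary to perform these procedures at unscheduled time points if deemed clinically necessary by the investigator".
- **What counts as progression.** Section 7.1.2.5: "The appearance of new lesions is considered PD according to RECIST v1.1".
- **Treatment after first progression.** Sections 5.7 and 7.1.2.5 tie mandatory discontinuation to confirmed radiographic progression and allow some subjects to continue past a first reading of progression.
- **Numbers.** Section 1.0 gives 29 subjects; section 5.8 allows no replacement.
- **Populations.** The only all-treated population in section 8.1 is for toxicity. The sentence on the ORR and its exact confidence interval names no denominator.

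**The concern.** Take a subject who deteriorates at week 4, has an unscheduled CT showing new liver lesions, and stops treatment. This subject has had fewer than 2 cycles, has progression on CT rather than on examination, and is alive, so no route applies. If the same progression had been palpable, the subject would have counted as a failure.

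The plan evidently means early failures to count, since it lists two kinds of them. Leaving out CT, the preferred assessment method in section 7.1.2.5, makes scoring depend on how the failure was found. The subject would have a PFS event under section 8.1 and yet be missing from the response denominator.

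Each subject lost this way is a non-responder. The numerator stays the same and the denominator shrinks, or the place is taken by someone who did not fail early in this way. With only 10 subjects in stage 1, one such substitution could change the decision to continue.

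**Working it through.** **Inputs from section 8.1:** p0 = 0.10, p1 = 0.30, n1 = 10, r1 = 1, N = 29, r = 5. **Assumption, not in the documents:** a share x of treated subjects, all non-responders, falls into the gap; range shown 3% to 20%.

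**Step 1. Reproduce the design.** The probability of declaring success at response rate p is

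Σ (a = 2 to 10) P[Bin(10, p) = a] × P[Bin(19, p) ≥ 6 − a].

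At p = 0.10 this is 0.0471, and at p = 0.30 it is 0.8051. P(stop at stage 1 | 0.10) = 0.9^10 + 10 × 0.1 × 0.9^9 = 0.3487 + 0.3874 = 0.7361, so P(pass stage 1) = 26.4%. An exhaustive search confirms this as the optimal design, with expected size 15.01 under p0. The design arithmetic is right.

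**Step 2. Stage 1 with the gap.** The response rate among evaluable subjects becomes q = 0.10/(1 − x), and P(pass stage 1) = P[Bin(10, q) ≥ 2].

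**Step 3. Type I error, two readings of the final sample.**

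- *29 treated in total.* Stage 1 closes at the M-th treated subject, when the 10th evaluable one is reached, with M − 10 negative binomial (10, 1 − x). The remaining 29 − M treated subjects each respond with probability 0.10, and success still needs 6 responses. The type I error is Σ over M and a ≥ 2 of P(M) × P[Bin(10, q) = a] × P[Bin(29 − M, 0.10) ≥ 6 − a].
- *Accrual to 29 evaluable.* Put q into the formula of step 1.

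| x | q | P(pass stage 1) | Type I error, 29 treated | Type I error, 29 evaluable |
|---|---|---|---|---|
| 0% | 0.1000 | 26.4% | 4.7% | 4.7% |
| 3% | 0.1031 | 27.6% | 4.8% | 5.3% |
| 5% | 0.1053 | 28.4% | 4.9% | 5.8% |
| 10% | 0.1111 | 30.7% | 5.1% | 7.1% |
| 15% | 0.1176 | 33.3% | 5.3% | 8.8% |
| 20% | 0.1250 | 36.1% | 5.5% | 11.0% |

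With 29 treated, the type I error is 4.98% at x = 7% and 5.02% at x = 8%, so it crosses 5% between the two.

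**Step 4. ORR estimate**, if the evaluable set is its denominator, with 6 responders among 29 treated and k excluded (exact 95% CI):

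| k | ORR | 95% CI |
|---|---|---|
| 0 | 6/29 = 20.7% | 8.0–39.7 |
| 1 | 6/28 = 21.4% | 8.3–41.0 |
| 2 | 6/27 = 22.2% | 8.6–42.3 |
| 3 | 6/26 = 23.1% | 9.0–43.6 |
| 4 | 6/25 = 24.0% | 9.4–45.1 |

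**The case against.** The affected group is small. Progression on the planned 6-week scan, after 2 cycles of both agents, already qualifies by the first route. To be lost, a subject must have an unscheduled CT before the end of cycle 2, stop before 2 cycles, show no clear progression on examination, and not die in that time. Subjects treated past a first reading of progression may complete 2 cycles and qualify. Those who decline fast enough to stop are also likely to have findings on examination or to die, and are then counted. All of this stands, and it limits the size of the effect.

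Three stronger readings are tempting and are not supported:

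- **That a fifth to a third of subjects are at risk of exclusion.** A reader might start from the 2.6-month median PFS on regorafenib in section 4.2.1.2. With exponential PFS, the share with an event in the 7 weeks (1.61 months) from the first lenvatinib dose to the first scan is 1 − 2^(−1.61/2.6) = 35%. That counts every early PFS event, including deaths, progression found on examination and progression on the planned scan, all of which are already evaluable. It does not estimate the gap.
- **That the type I error exceeds 5%.** With 29 treated it does so only above about 7% excluded. The 5.3–11.0% column requires enrolment beyond 29, contrary to sections 1.0 and 5.8. Section 8.1's reference to 29 response-evaluable subjects pulls the other way, but that conflict is a separate matter.
- **That the published ORR will be inflated.** Only the decision bounds are tied to evaluable subjects. The estimate is inflated only if the unstated denominator is the evaluable set, and even 24.0% lies well inside the 8.0–39.7 interval.

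**Conclusion.** The point holds as a gap in a stated rule. No text elsewhere brings the early CT-only progressor back into the decision sets. The direction is certain, because every subject lost is a non-responder. The size is not known: the 3–20% range is an assumption, and the true share may lie at its low end or below.

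The more sensitive quantity is stage 1, where the chance of continuing with a drug at the null rate rises by 1.2 percentage points at 3% excluded (27.6 − 26.4) and by 9.7 at 20% (36.1 − 26.4). The effect on the type I error with 29 treated is under one point throughout. The change is worth making because the remedy is cheap and removes discretion over who counts, not because a large bias has been shown.

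**What to change.** In section 8.1, replace the physical-examination condition with *disease progression by any method (RECIST 1.1 on scheduled or unscheduled imaging, or clear clinical progression)* before completing 2 cycles, keeping early death as it is. State that these subjects count as non-responders at stage 1 and in the final decision. As far as this gap is concerned, that restores the design values of 0.0471 and 0.8051.

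Name the denominator of the ORR and its exact confidence interval, and report the ORR in all treated subjects as well, with those lacking a post-baseline scan counted as non-responders. The second analysis is needed because the definition also omits subjects who stop before 2 cycles for toxicity, withdrawal or decline without examination findings, and the changed phrase alone would not bring all of them in.

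The cost is a changed phrase and a short addition to section 8.1. No new data or procedures are needed. The reported ORR may be slightly less favourable.

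### Does the exact 95% interval for response rate conflict with the two-stage rule because it contains 10% at the smallest success, 6 of 29?

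*Combined protocol and SAP*

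**What the plan says.** All of this stands in Section 8.1. The design tests a 10% response rate against an "alternative hypothesis of >30% overall response rate", with 29 subjects "in order to achieve 80% power with a significance level of 5" per cent. After 10 response-evaluable subjects "the trial will be terminated if there are 1 or fewer responses". At the end, 5 or fewer responses in 29 reject the combination. "If there are 6 or more responses (including non-confirmed responses) over the entire treatment duration", it is taken forward.

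For estimation there is one sentence: "Overall response rates (defined as PR plus CR) will be estimated with exact 95% confidence intervals". It names no method, does not mention the stage 1 stop, and does not link the interval to the decision. Nothing else in Section 8.1 uses the interval to judge success.

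**The concern.** Response rate is the primary objective (Section 3.1), so this will be the trial's headline interval. Two features of the test do not carry over to it.

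- The 5% level is one-sided, whereas a 95% two-sided interval puts 2.5% in each tail.
- The test stays below 5% only because of the stop at 1 or fewer of 10. A fixed-sample interval ignores that stop.

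A trial that only just succeeds, at 6 of 29, would therefore be reported as having rejected 10% beside an interval that includes 10%. A reader might think the analysis contradicts itself. If the analyst chose the interval method after seeing six responses, the choice could look selective. The natural remedy is to prescribe an exact interval from the two-stage sampling distribution and add one at the 90% level.

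**Working it through.** **Inputs (Section 8.1).** n1 = 10, stop if X1 ≤ 1; n = 29, so 19 subjects in stage 2; success if the total S ≥ 6; null rate 0.10, target rate 0.30.

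**The plan's own figures.** P(success | p) = Σ over x = 2,…,10 of P(X1 = x | 10, p) × P(X2 ≥ 6 − x | 19, p).

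- p = 0.10: 0.0471.
- p = 0.30: 0.805.
- Probability of stopping at stage 1 at p = 0.10: 0.9^10 + 10 × 0.1 × 0.9^9 = 0.3487 + 0.3874 = 0.736.

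A search at one-sided 5% and 80% power returns exactly 1/10 and 5/29 as the optimal design. At one-sided 2.5% it returns 1/10 and 7/38. The text does not state sidedness, but the stated design is a one-sided 5% design. Without the stage 1 stop, P(X ≥ 6 of 29 | 0.10) would be 0.0637.

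**Intervals at the boundary.** Clopper-Pearson limits are the α/2 quantile of Beta(x, n − x + 1) and the 1 − α/2 quantile of Beta(x + 1, n − x). Stage-wise limits solve P(X1 ≥ 2, S ≥ s | p) = α/2 for the lower limit and 1 − P(X1 ≥ 2, S ≥ s + 1 | p) = α/2 for the upper.

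| Result | Method | 95% interval | 90% interval |
|---|---|---|---|
| 6/29 | Clopper-Pearson | 8.0–39.7% | 9.4–36.8% |
| 6/29 | Stage-wise | 8.6–45.5% | 10.15–41.3% |
| 7/29 | Clopper-Pearson | 10.3–43.5% | 11.9–40.6% |

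At 6/29 only the stage-wise method and the 90% level together exclude 10%. Other fixed-sample exact methods do not help: the Blaker and Sterne 95% lower limits are both about 9.4%. So every exact 95% interval examined contains 10% at 6/29, whichever method the analyst picks.

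**How often this arises.**

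| True rate | P(S = 6) | P(success) | Share of successes |
|---|---|---|---|
| 10% | 0.0294 | 0.0471 | 62% |
| 20% | 0.1253 | 0.4314 | 29% |
| 30% | 0.0662 | 0.8051 | 8% |

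**Is the usual interval valid under this design?** Clopper-Pearson is applied to X1/10 after an early stop and to S/29 otherwise, with coverage summed over the two-stage distribution. Coverage of the 95% interval is 98.2%, 98.1% and 98.6% at 10%, 20% and 30%. The stage-wise interval has the same coverage at 10% and 20%.

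**What the stage-wise interval would cost.** Averaged over all trials, the 95% width goes from 0.353 to 0.383 at a true rate of 10%, and from 0.352 to 0.385 at 20%. The two methods agree after a stage 1 stop, so the whole difference falls on trials that continue:

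- At 10%, P(continue) = 1 − 0.736 = 0.264, and 0.030 / 0.264 ≈ 0.115 of extra width.
- At 20%, P(continue) = 1 − 0.8^10 − 10 × 0.2 × 0.8^9 = 1 − 0.1074 − 0.2684 = 0.624, and 0.033 / 0.624 ≈ 0.05.

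| Failed result | Clopper-Pearson 95% | Stage-wise 95% |
|---|---|---|
| 2/29 | 0.8–22.8% | 2.5–44.5% |
| 3/29 | 2.2–27.4% | 3.5–44.5% |
| 5/29 | 5.8–35.8% | 6.7–44.8% |

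At 2/29 and 3/29 the Clopper-Pearson interval excludes the 30% target; the stage-wise interval does not.

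**The case for a change.** The best case for a change is that it is cheap. One sentence could name the method, and another could add the stage-wise 90% interval or its equivalent one-sided 95% lower bound (10.15% at 6/29), which agrees with the rule. Six of 29 is the smallest success and so a large share of successes when the true rate is modest. Reading success off the Clopper-Pearson interval instead would move the bar to 7 of 29, with type I error 0.0177 and power 0.739, which is not the planned test.

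The facts in that case stand: the method is unnamed, and at 6/29 the interval and the rule will appear to disagree. The need for a change does not follow. Section 8.1 already makes the count decisive, so nobody following it would read success off the interval. The 62% figure is a share of an event with probability 4.7%. Naming the stage-wise method alone leaves 10% inside the 95% interval. Making it the main interval would swap one awkward appearance at 6/29 for another in failed trials, where it would no longer exclude the target. A companion 90% bound would be harmless, but it would alter no decision and no planned estimate.

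It can also be said that fewer than 29 subjects may prove response evaluable, since Section 5.8 states that "There are no replacement subjects allowed". That concerns the denominator and the decision rule. It does not bear on which exact method is used.

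**Conclusion.** No change is needed. The plan leaves out a detail that an analyst would ordinarily fill with Clopper-Pearson, and that choice is sound here: coverage is at least 98% at true rates of 10%, 20% and 30%, and the decision rests on counts with type I error 0.0471 and power 0.805. The apparent conflict comes from setting a two-sided 95% interval beside a one-sided 5% test. It affects one successful count, 6 of 29, with probability between 2.9% and 12.5% at the three rates examined. The proposed replacement gains no coverage at 10% or 20%, does not remove 10% from the 95% interval, and widens it by about 0.115 (at 10%) or 0.05 (at 20%) in trials that reach stage 2. Saying in the report that success was judged on the count deals with the appearance.

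This rests on three assumptions: the 5% level is one-sided, as the design arithmetic shows; the stages are run at 10 and 29 evaluable subjects; and exact means Clopper-Pearson or a comparable exact binomial method.
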